### **3. STUDY DESIGN**

#### **3.1 Study Description and Duration**

This prospective, open-label, single-center, randomized, investigator-initiated clinical study seeks to investigate the safety and efficacy of the DEXTENZA insert in pediatric patients following retinal surgery or laser treatment under anesthesia.

### **4. SELECTION, WITHDRAWAL, AND REPLACEMENT OF PATIENTS**

#### **4.1 Study Population**

The study aims to enroll 30 pediatric patients undergoing routine retinal surgery or laser treatment under anesthesia. Patients in each treatment group (surgery or laser) will be randomized 2:1 at the time of surgery/laser to receive either:

- 3) Treatment Arm: Dextenza insert intraoperatively for perioperative ocular inflammation and pain. These patients will not be prescribed topical steroid drops post-operatively, or
- 4) Control Arm: Prednisolone forte 1% steroid drop taper for 28 days post-operatively to treat perioperative ocular inflammation and pain; drops four times per day (QID) on days 0-7, three times per day (TID) on days 7-14, twice per day (BID) on days 14-21 and once per day (QD) on days 21-28.

Each treatment group (surgery or laser) will include 15 patients total, 10 receiving Dextenza and 5 receiving the control drug. Drops for dilation and antibiotic coverage will be used as clinically indicated in all groups throughout the study period. Follow up will occur at post-op day 1, 7, 28/30 and 45 (+/- three days for all post-operative timepoints).

##### **4.1.1 Inclusion Criteria**

A patient's study eye must meet the following criteria to be eligible for inclusion in the study:

- 3 to <17 year old pediatric patients undergoing routine retinal surgery or laser treatment under anesthesia for a variety of visual conditions. These conditions and procedures include but are not limited to:
  - Conditions:
    - Familial Exudative Vitreoretinopathy
    - Coats' Disease
    - Exudative Retinopathy
    - Lattice degeneration
    - Retinal holes
    - Sickler's syndrome
    - Retinal detachment, rhegmatogenous
    - Retinal detachment, exudative
    - Retinal detachment, tractional
  - Procedures
    - Laser photocoagulation
    - Cryotherapy
    - Retinal detachment repair with scleral buckle and cryotherapy
    - Retinal detachment repair with vitrectomy
- Written informed consent from parent/legal guardian

#### 4.1.2 Exclusion Criteria

A patient who meets any of the following criteria will be excluded from the study:

##### **Preprocedural**

- Subjects needing laser or ocular surgery in the fellow eye concurrently as the study eye.
- Active or history of chronic or recurrent inflammatory eye disease in either eye
- Any patient of reproductive potential that has a positive pregnancy test during pre-procedural testing
- Active or history of increased ocular pressure
- Patients with active corneal, conjunctival, and canalicular infections
- Patients with punctal stenosis or other punctal anatomical abnormalities that would not be conducive with device insertion
- Nasolacrimal duct obstruction
- Laser or incisional ocular surgery during the study period and 3 months prior in the study eye
- current use of systemic or topical steroids or NSAIDS on a regular basis

- History of autoimmune disease that may interfere with treatment/outcomes
- Ocular pain at the time of screening
- Known malignancy
- Current use of cyclosporin or a TNF blocker
- Ocular hypertension IOP >25, actively taking medications for ocular hypertension, any history of IOP spikes in either including steroid associated IOP elevation
- Congenital ocular lid and tear duct system abnormalities (e.g. congenital ectropion/entropion, trichiasis)
- Evidence of acute external ocular infection of the study eye
- Active or history of HSV
- Previous trauma causing deformity
- Previous enrollment or current enrollment with another clinical trial within the last 30 days that may interfere with treatment
- Known allergies to product under investigation
- Inability to engage in VA testing
- Investigator determines that the candidate is not eligible for participation based on clinical or historical factors that would interfere with treatment or impact patient safety not specified above
- Current artificial tear use >4x daily
- Anyone who, in the opinion of the investigator, would not be a good candidate for the study.

#### **Intraoperatively**

- Multiple and/ or extensive procedures required at the surgeon's discretion.
- Complication occurs that surgeon determines makes the patient ineligible for study inclusion
- Unsuccessful dilation of the punctum to 0.7mm when dilation attempted
- During the exam under anesthesia, if it is decided that periocular Kenalog injection is indicated this patient fails screen and will no longer be eligible for the study

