**Table 1 Treatment Arm Schedule of Events**

Study Procedure	Screening/ Baseline	Surgical Visit Day 0	Day 1	Day 7	Day 28	Day 45
Visit	VISIT 1	VISIT 2	VISIT 3	VISIT 4	VISIT 5	VISIT 6
Windows for Visits	(Day -30 to 0)		+/- 3 days	+/- 3 days	+/- 3 days	+/- 3 days
Inclusion/Exclusion	X					
Informed Consent	X					
Demographics	X					
Medical History and Concurrent Illnesses	X					
Concomitant Medications	X					
Pregnancy testing as indicated/appropriate		X				
Subject reported AEs prior to or after surgery	X	X	X	X	X	X
Randomization with subsequent intracanalicular dexamethasone insert placement		X				
Easy of insertion		X				
If dilator was used		X				
Document administration of prescribed medications			X	X	X	X
Ocular Pain Assessment (FLACC)	X		X	X	X	X
Distance VA testing	X		X	X	X	X
BCVA (ETDRS at 4m)	X		X	X	X	X
Anterior chamber cell count	X		X	X	X	X

Study Procedure	Screening/ Baseline	Surgical Visit Day 0	Day 1	Day 7	Day 28	Day 45
Visit	VISIT 1	VISIT 2	VISIT 3	VISIT 4	VISIT 5	VISIT 6
Windows for Visits	(Day -30 to 0)		+/- 3 days	+/- 3 days	+/- 3 days	+/- 3 days
Anterior chamber cell flare	X		X	X	X	X
Punctum examination	X	X	X	X	X	X
Insert Visualization and ease of visualization score			X	X	X	X
Intraocular Pressure	X		X	X	X	X
Ophthalmic Examination (dilated fundus exam)	X		X	X	X	X
Satisfaction Survey						X

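### Failed punctal dilation can remove randomised children from the Dextenza arm only, and no analysis set keeps them in

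*Combined protocol and SAP*

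**What the plan says.** Section 4.1 sets the timing of allocation: "Patients in each treatment group (surgery or laser) will be randomized 2:1 at the time of surgery/laser to receive either" the insert or the prednisolone taper. It gives the numbers as "Each treatment group (surgery or laser) will include 15 patients total, 10 receiving Dextenza and 5 receiving the control drug".

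Table 1 (insert arm) lists, on Day 0, "Randomization with subsequent intracanalicular dexamethasone insert placement". It also has rows for ease of insertion and for whether a dilator was used. Table 2 (control arm) has randomisation and a punctum examination on Day 0, but no row for dilation or insertion.

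Section 4.1.2 opens with "A patient who meets any of the following criteria will be excluded from the study". Its intraoperative list includes "Unsuccessful dilation of the punctum to 0.7mm when dilation attempted" and "Complication occurs that surgeon determines makes the patient ineligible for study inclusion". It also has one item on multiple or extensive procedures, left to the surgeon, and one on a periocular steroid injection, worded as a screen failure.

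Section 8.1 presents results by arm, overall and by procedure group, and calls the trial an unpowered feasibility study. Section 8.1.1 summarises disposition and exposure for study patients. Neither defines an analysis set or says how a child excluded after allocation is handled. The title of section 4 mentions replacement, but no replacement rule follows.

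**The concern.** An exclusion that acts after allocation and in one arm only undoes what randomisation provides. Children whose puncta cannot be dilated would leave the insert arm. Children with the same anatomy in the control arm would stay, because nobody tries to dilate them. If these children differ in age, anatomy or post-operative course, the remaining groups differ for reasons other than treatment.

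The second loss is descriptive. An unpowered feasibility study of an insert should show how often the insert could be placed among those assigned to it. A child with a failed dilation also had an attempted instrumentation of the punctum, and section 6.1.3 lists punctal trauma as an event of special interest. Nothing says that such a child is followed to Day 45, so an injury from the attempt could fall outside the safety summary.

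**Working it through.** **1. The plan's own numbers.** Two procedure groups of 15 give 2 × 15 = 30. Splitting 15 in the ratio 2:1 gives 10 and 5, so the arms are 2 × 10 = 20 and 2 × 5 = 10. This reproduces section 4.1. There is no power calculation to reproduce, because no alpha, power, effect size or SD is stated.

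**2. When and where the criterion can be met.**
- Section 4.1: randomisation is at the time of the procedure.
- Table 1: insertion follows randomisation.
- Table 1 against Table 2: dilator use is recorded in the insert arm only, and the control arm has only a punctum examination.
- The criterion applies only when dilation is attempted.

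Dilation is therefore a step of insertion, and insertion comes after allocation in one arm. Of the 30 children, the criterion can reach the 20 assigned to the insert and none of the 10 controls.

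**3. How many children.** The documents give no dilation failure rate. I assume a rate f between 2% and 20%. Expected losses are 20f, and P(at least one) = 1 − (1 − f)^20.

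| Assumed f | Expected losses of 20 | P(at least one) |
|---|---|---|
| 2% | 0.4 | 33% |
| 5% | 1.0 | 64% |
| 10% | 2.0 | 88% |
| 15% | 3.0 | 96% |
| 20% | 4.0 | 99% |

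**4. Effect on reported insertion success.** Take failed dilation as the only reason for failure. With k failures, success among those assigned is (20 − k)/20. After exclusion it is (20 − k)/(20 − k).

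| k | All assigned | After exclusion |
|---|---|---|
| 1 | 19/20 = 95% | 19/19 = 100% |
| 2 | 18/20 = 90% | 18/18 = 100% |
| 3 | 17/20 = 85% | 17/17 = 100% |
| 4 | 16/20 = 80% | 16/16 = 100% |

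**5. Effect on a mean outcome.** Suppose the failures differ from the other insert-arm children by D standard deviations. Excluding them shifts the insert-arm mean by f × D. For D = 0.5 to 1.0 (assumed):
- f = 5%: 0.025 to 0.05 SD
- f = 10%: 0.05 to 0.10 SD
- f = 20%: 0.10 to 0.20 SD

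With equal SDs, the standard error of the 20 versus 10 difference is SD × √(1/20 + 1/10) = 0.39 SD. The largest shift, 0.20 SD, is about half of one standard error (0.20/0.39 = 0.5).

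**The case against.** Several points on the other side have force.

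- **The order of the other checks.** A reader might infer that all the intraoperative exclusions act after allocation. The documents do not support that. The steroid-injection item is worded as a screen failure, the complication item speaks of eligibility for inclusion, and section 5.2.1 lists the Day 0 punctum examination before randomisation. The same list puts the recording of surgical complications after randomisation. The order is simply not stated. Only the dilation criterion is tied to a step after allocation.
- **Failures do not vanish from the record.** Ease of insertion, dilator use, insert accountability (section 4.2.2) and disposition (section 8.1.1) may all show them. That stands. However, disposition covers study patients, and a child excluded from the study is not clearly one of them.
- **Placement success is not a listed endpoint.** That is correct, so no stated result is being removed. The term feasibility is used in section 8.1 to explain the lack of power.
- **The comparison need not be biased.** The analysis is descriptive, and section 4.1.2 already excludes punctal stenosis, unsuitable punctal anatomy and nasolacrimal obstruction, which should lower the failure rate. A reader might quote an overstatement of 4, 8 or 12 percentage points in a resolution rate (0.8 × k/20 for k = 1, 2, 3). That requires an assumed 80% rate, an assumed number of removals and every removed child counted as unresolved. None of these is in the documents, and resolution is a secondary endpoint.
- **Re-operation.** The item "Laser or incisional ocular surgery during the study period and 3 months prior in the study eye" might be read as removing children who need re-operation. It stands under the preprocedural criteria, and nothing says it would be applied later. It is loose drafting and not part of this point.

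None of this answers the one-arm exclusion after allocation.

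**Conclusion.** The point holds for failed dilation. Following the text as written, this criterion can remove randomised children from the Dextenza arm and cannot remove controls, and no analysis set keeps those removed in the results. The comparison can be biased; the documents do not show that it is.

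The size is unknown. The direct effect is on what the results show about placement: with 1 to 4 failures among 20, the analysed children would show none of them. The effect on mean outcomes is probably small relative to the standard error, given the assumed ranges (f up to 20%, D up to 1 SD). The conclusion rests on reading dilation as part of insertion, which the two schedules support but do not state outright. For the complication and extensive-procedure items, the finding is only that their order relative to randomisation is missing.

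**What to change.** Amend sections 4.1, 4.1.2 and 8.1 and Tables 1 and 2:

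1. The surgeon confirms and records all intraoperative criteria other than dilation before the allocation is revealed.
2. No child is excluded after allocation. A failed dilation is recorded as an insertion failure, and the child stays in follow-up to Day 45 and is analysed in the assigned arm.
3. Insertion success is reported with all children assigned to the insert as the denominator.

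One clinical passage must be reconciled at the same time. Section 4.1 says that insert-arm children are not prescribed topical steroid drops, and section 5.3 leaves rescue to the surgeon. Neither addresses a child assigned to the insert who does not receive it. The protocol has to say what applies; that choice belongs to the investigator.

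The cost is protocol wording, a recorded eligibility check before allocation, and continued follow-up of any child with a failed dilation. The insert arm may look slightly less favourable because it will include children who did not receive the insert.

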## **4.2 Treatment Logistics and Accountability**

### **4.2.1 Packaging, Labeling, and Storage**

Intracanalicular dexamethasone insert must be stored in a secure area accessible only to the Investigator and their designee(s) and refrigerated and stored between 2° C and 8° C. Intracanalicular dexamethasone insert contains 0.4 mg dexamethasone and is designed to provide a sustained and tapered release of therapeutic levels of dexamethasone to the ocular surface for up to 30 days for the reduction of post-surgical inflammation and pain associated with ocular surgery. Dexamethasone is an anti-inflammatory 9-fluoro-glucocorticoid (also termed a glucocorticoid agonist) and is the active ingredient found in

MAXIDEX® 0.1% (dexamethasone ophthalmic suspension), which contains approximately 50 µg of dexamethasone per drop.

Study inserts will be supplied by Ocular Therapeutix in a sealed foil pouch containing one intracanalicular dexamethasone insert in a foam carrier.

Study inserts will be shipped to the site via overnight shipping using cold packs to maintain a temperature of 2° to 8° C. The Investigator, or an approved representative (e.g. pharmacist), will ensure that all study drug inserts are stored in a secured area, under recommended storage conditions and in accordance with applicable regulatory requirements. The shipping box is to be opened and stored immediately at the site in a refrigerator intended for investigational products at a temperature of 2° to 8°C.

When the insert is removed from the refrigerator, it should be visually inspected. Exposure of the insert to temperatures outside these limits is not recommended. Records of actual storage conditions (i.e. temperature log) at the study site must be maintained; and must include a record of the dates, when the refrigerator was checked, the initials of person checking, and the temperature.

#### **4.2.2 Treatment Accountability**

All study insert accountability records will be kept current.

The investigator will account for all opened and unopened packaging of study inserts. These records will contain the dates, quantity, and study medication

- Inserted in each patient,
- disposed of at the site or returned to Ocular Therapeutix

All accountability records will be made available for inspection by regulatory agency inspectors.

#### **4.3 Concomitant Medications and Procedures**

At the discretion of their physician, patients may continue to receive all medications and standard treatments administered for other conditions. Antibiotic regimen will not exceed 4x daily and will be the same in both treatment groups/arms.

Removal of insertion should occur if based on examination it is determined that patient is having AE directly related to DEXTENZA implant.

## **5. STUDY SCHEDULE OF EVENTS AND VISIT DESCRIPTIONS**

### **5.1 Schedule of Events**

Study assessments and procedures are presented by visit in Table 1 (treatment arm schedule of events) and Table 2 (control arm schedule of events).

**Table 1 Treatment Arm Schedule of Events**

Study Procedure	Screening/ Baseline	Surgical Visit Day 0	Day 1	Day 7	Day 28	Day 45
Visit	VISIT 1	VISIT 2	VISIT 3	VISIT 4	VISIT 5	VISIT 6
Windows for Visits	(Day -30 to 0)		+/- 3 days	+/- 3 days	+/- 3 days	+/- 3 days
Inclusion/Exclusion	X					
Informed Consent	X					
Demographics	X					
Medical History and Concurrent Illnesses	X					
Concomitant Medications	X					
Pregnancy testing as indicated/appropriate		X				
Subject reported AEs prior to or after surgery	X	X	X	X	X	X
Randomization with subsequent intracanalicular dexamethasone insert placement		X				
Easy of insertion		X				
If dilator was used		X				
Document administration of prescribed medications			X	X	X	X
Ocular Pain Assessment (FLACC)	X		X	X	X	X
Distance VA testing	X		X	X	X	X
BCVA (ETDRS at 4m)	X		X	X	X	X
Anterior chamber cell count	X		X	X	X	X

Study Procedure	Screening/ Baseline	Surgical Visit Day 0	Day 1	Day 7	Day 28	Day 45
Visit	VISIT 1	VISIT 2	VISIT 3	VISIT 4	VISIT 5	VISIT 6
Windows for Visits	(Day -30 to 0)		+/- 3 days	+/- 3 days	+/- 3 days	+/- 3 days
Anterior chamber cell flare	X		X	X	X	X
Punctum examination	X	X	X	X	X	X
Insert Visualization and ease of visualization score			X	X	X	X
Intraocular Pressure	X		X	X	X	X
Ophthalmic Examination (dilated fundus exam)	X		X	X	X	X
Satisfaction Survey						X

**Table 2 Control Arm Schedule of Events**

Study Procedure	Screening/ Baseline	Surgical Visit Day 0	Day 1	Day 7	Day 28	Day 45
-----------------	------------------------	-------------------------	-------	-------	--------	--------

Visit	VISIT 1	VISIT 2	VISIT 3	VISIT 4	VISIT 5	VISIT 6
Windows for Visits	(Day -30 to 0)		+/- 3 days	+/- 3 days	+/- 3 days	+/- 3 days
Inclusion/Exclusion	X					
Informed Consent	X					
Demographics	X					
Medical History and Concurrent Illnesses	X					
Concomitant Medications	X					
Pregnancy testing as indicated/appropriate		X				
Subject reported AEs prior to or after surgery	X	X	X	X	X	X
Randomization without intracanalicular dexamethasone insert placement		X				
Document administration of prescribed medications			X	X	X	X
Ocular Pain Assessment (FLACC)	X		X	X	X	X
Distance VA testing	X		X	X	X	X
BCVA (ETDRS at 4m)	X		X	X	X	X
Anterior chamber cell count	X		X	X	X	X
Anterior chamber cell flare	X		X	X	X	X
Punctum examination	X	X				
Intraocular Pressure	X		X	X	X	X

Study Procedure	Screening/ Baseline	Surgical Visit Day 0	Day 1	Day 7	Day 28	Day 45
Visit	VISIT 1	VISIT 2	VISIT 3	VISIT 4	VISIT 5	VISIT 6
Windows for Visits	(Day -30 to 0)		+/- 3 days	+/- 3 days	+/- 3 days	+/- 3 days
Ophthalmic Examination (dilated fundus exam)	X		X	X	X	X
Satisfaction Survey						X

## **5.2 Study Visit Descriptions for control and treatment arms**

### **5.2.1 Study Procedures**

#### **Visit 1 (Day -30 to 0) Screening/Baseline**

After the patient has provided informed consent, the following information will be collected:

- Inclusion/exclusion
- Demographics
- Medical history and concurrent illnesses
- Concomitant medications
- Subject reported AE's prior to surgery
- Ocular Pain Assessment (FLACC)
- Distance VA testing, when applicable
- Best-corrected visual acuity as measured by ETDRS or HOTV chart at 4m based on patient age (HOTV for pre-literate patients)
- Anterior chamber cell count
- Anterior chamber cell flare
- Punctum examination
- Intraocular pressure
- Ophthalmic Examination including dilated fundus exam

#### **Visit 2 Surgical Visit ( Day 0)**

- Subject reported AE's prior to surgery
- Indicate the incision type, location, and size (mm)
- Punctum examination
- If you are a patient who could possibly be pregnant (you have started menstruation), a urine pregnancy test will be performed, and it must be negative in order to continue in the study.
- Randomization and potential placement of intracanalicular dexamethasone insert if assigned to treatment arm
- Record any surgical complications

**Visit 3 (Day 1 +/- 3 days) Visit 4 (Day 7 +/- 3 days) Visit 5 (Day 28 +/- 3 days)  
Visit 6 (Day 45 +/- 3 days)**

- Subject reported AE's after surgery
- Document administration of prescribed medication (if used and number of drops used)
- Ocular Pain Assessment (FLACC)
- Distance VA testing, when applicable
- Best-corrected visual acuity as measured by ETDRS or HOTV chart at 4m based on patient age (HOTV for pre-literate patients)
- Anterior chamber cell count
- Anterior chamber cell flare
- Punctum examination and ease of insert visualization (for patients receiving DEXTENZA insert only)
- Intraocular pressure
- Ophthalmic Examination including dilated fundus exam
- Satisfaction Survey (at the end of visit 6 only)

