**Clinical Study Protocol Synopsis**

Title	The Evalua T ion of the Safety and E fficacy of Sustai N ed Release D examethasone Intra c analicular In s ert (DEXTENZA) in p E diatric patients following R etinal surgery or laser treatment under anesthesia
Site Location(s)	Duke University Eye Center
Principal Investigator	[name]
Objective(s)	To determine safety and efficacy of the dexamethasone ophthalmic insert in pediatric patients following retinal surgery or laser treatment under anesthesia
Study Design	Prospective Open-label Interventional Study
Study Duration	45 days postoperative
Estimated Study Completion Date	August 1, 2023
Population	
Sample Size:	30
Target Population:	Pediatric patients ages 3 to 17 undergoing routine retinal surgeries or laser treatment under anesthesia
Study Drug	DEXTENA (dexamethasone ophthalmic insert) 0.4 mg, for intracanalicular use
Dose/Route/Schedule:	
All eyes will undergo routine retinal surgery or laser treatment under anesthesia.
 
Patients in each treatment group (surgery or laser) will be randomized 2:1 at the time of surgery/laser to either:
 
 
1) Treatment Arm: Dextenza insert intraoperatively for perioperative ocular inflammation and pain. These patients will not be prescribed topical
 

steroid drops post-operatively, or

- 2) Control Arm: Prednisolone forte 1% steroid drop taper for 28 days post-operatively to treat perioperative ocular inflammation and pain; drops four times per day (QID) on days 0-7, three times per day (TID) on days 7-14, twice per day (BID) on days 14-21 and once per day (QD) on days 21-28.

Each treatment group (surgery or laser) will include 15 patients total, 10 receiving Dextenza and 5 receiving the control drug.

Drops for dilation and antibiotic coverage will be used as clinically indicated in all groups and arms.

There will be a total of six visits for both treatment arms Screening/Baseline visit (day -30 to 0), Surgical Visit (day 0), and four post-operative follow up appointments occurring at post-op day 1, 7, 28/30 and 45 ( +/- three days for all post-operative timepoints). Exams to be performed on these days are outlined in section 5.1.. Treatment Arm Schedule of Events in Table 1. Control Arm Schedule of Events in Table 2

---

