## Endpoint(s)

### Primary Endpoint:

To evaluate if pediatric patients receiving retinal surgery or laser would benefit from DEXTENZA implant compared to topical ocular drop therapy to manage post-operative pain (measured with the Face, Legs, Activity, Cry Consolability (FLACC) Behavioral Pain Rating Scale). Pain will be measured at each visit with final outcome determined by the FLACC Pain Rating Scale score on day 45 (final visit).

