### 2.2 Secondary Objectives

- Incidence and severity of adverse events from baseline through post-op day 45
- Degree of inflammation (AC cell count)
- Resolution of inflammation as defined as either 0 or 0.5 or less cell on follow up post op exams
- Resolution of pain using the FLACC Behavioral Pain Rating Scale
- Ratio of Intraocular pressure increase with insert
- % of patients with rebound inflammation from baseline through post-op care
- % of patients that were given supplementary prednisolone drops and the number of drops needed in these patients

- Mean change in BCVA from baseline over time using either ETDRS or HOTV chart testing depending on age
- Primary caregiver's ability to adhere to treatment plan as prescribed and therapeutic preferences measured with primary caregiver satisfaction survey

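### The ±3-day window for Visit 3 (Day 1) overlaps the Day 7 window and lets the first post-operative pain and inflammation reading fall as late as Day 4

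*Combined protocol and SAP*

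**What the plan says.** Section 5.2.1 fixes the time origin at the operation: "Visit 2 Surgical Visit ( Day 0"). It then gives the follow-up windows, beginning "Visit 3 (Day 1 +/- 3 days) Visit 4 (Day 7 +/- 3 days"). Section 4.1 states the tolerance as a blanket rule: "Follow up will occur at post-op day 1, 7, 28/30 and 45 (+/- three days for all post-operative timepoints"). The synopsis does the same ("three days for all post-operative timepoints"), and the window rows of Tables 1 and 2 repeat it for both arms.

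Both tables schedule FLACC and anterior chamber cells at baseline and at Visits 3 to 6, but not at Visit 2 (Day 0). The Visit 2 list in Section 5.2.1 omits them too.

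For the primary endpoint the synopsis says "Pain will be measured at each visit with final outcome determined by the FLACC Pain Rating Scale score on day 45 (final visit"). Resolution of pain and degree of inflammation are secondary endpoints, as is "Resolution of inflammation as defined as either 0 or 0.5 or less cell on follow up post op exams".

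Section 8.1 plans descriptive summaries by arm, overall and by procedure group. Nothing in the protocol cuts the Visit 3 window off at surgery, sets a minimum gap between Visits 3 and 4, or says which visit a Day 4 assessment belongs to.

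**The concern.** A tolerance of three days is modest around Day 28 or Day 45. Around Day 1 it is three times the distance from surgery, so the window reaches back before the operation and forward to the edge of the next visit.

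The backward reach conflicts with the visit's own content. Visits 3 to 6 collect "Subject reported AE's after surgery", and in the treatment arm they look for the insert. Neither is possible before surgery.

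The forward reach matters more. Section 4.1.2 excludes children with ocular pain at screening, so post-operative pain is first expected to show at Visit 3. If that visit may fall on Day 4, the summary labelled Day 1 can mix children seen the morning after surgery with children seen several days into recovery and treatment. Any statement about when pain or inflammation resolved then rests on an early time point that is loosely defined. By-visit description is much of what a feasibility study of this kind will report.

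**Working it through.** **Inputs.** Surgery is Day 0 (Section 5.2.1). The nominal follow-up days are 1, 7, 28 (28/30 in the synopsis and Section 4.1) and 45. The tolerance is ±3 days at each. The baseline window is Day -30 to Day 0 ("Visit 1 (Day -30 to 0) Screening/Baseline").

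**Windows.** Window = nominal day - 3 to nominal day + 3.

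| Visit | Nominal day | Window |
|---|---|---|
| 3 | 1 | 1 - 3 = -2 to 1 + 3 = 4 |
| 4 | 7 | 7 - 3 = 4 to 7 + 3 = 10 |
| 5 | 28 (or 30) | 25 to 31 (or 27 to 33) |
| 6 | 45 | 42 to 48 |

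**Overlap of neighbouring windows.**
- Visits 3 and 4 share exactly one day, Day 4.
- Visits 4 and 5 share none (10 is before 25).
- Visits 5 and 6 share none (33 is before 42).

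The problem is confined to the first pair.

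**Content of the Visit 3 window.** It has seven days: two before surgery (Day -2 and Day -1), the day of surgery, and four after it (Days 1 to 4). Days -2 to 0 also lie inside the baseline window.

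**Sensible reading.** Suppose Visit 3 must follow surgery. The reading labelled Day 1 can still come from any day from 0 to 4. The gap between Visits 3 and 4, nominally 7 - 1 = 6 days, can run from 4 - 4 = 0 to 10 - 0 = 10 days.

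**A compliant schedule that shows the gap.** Surgery on Day 0, Visit 3 on Day 4, Visit 4 on Day 7. Both visits are in window, and no FLACC or anterior chamber cell reading exists for Days 1, 2 or 3.

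**Check of a replacement.** A Visit 3 window of Day 1 to Day 3 contains no pre-surgery day and has no day in common with Day 4 to Day 10. Its width, latest minus earliest day, falls from 4 - 0 = 4 days on the sensible reading to 3 - 1 = 2 days.

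**The case against.** The strongest reply is that this takes a general tolerance too literally.

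- **Pre-surgery days.** The visits are called post-operative and are numbered in sequence after the surgical visit, so no site would hold Visit 3 before the operation. This stands. The pre-surgery days are a wording fault, not an operating risk.
- **The Day 4 overlap.** If Visit 3 has already taken place, a Day 4 attendance would naturally be Visit 4; if not, it would be Visit 3. This largely stands, since ambiguity needs a missed or late Visit 3. The plan does not state that convention, however, and the convention does nothing about a Day 4 reading being summarised as Day 1.
- **Day 1 remains the target.** Section 5.2.2 asks that children be kept on schedule. That makes late visits less frequent, but they remain compliant when they occur.

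Two stronger readings are tempting, and the documents support neither. A reader might infer that the primary outcome is compromised. It is the Day 45 score, with a window of Day 42 to Day 48 that overlaps nothing.

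A reader might also infer that differences in visit timing could pass for a treatment effect in an open-label trial. Both arms have the same windows, allocation is randomised, Appendix 10.3 has FLACC scored by masked personnel, and nothing in the plan suggests that Visit 3 would run later in one arm. Section 8.1 also says the study is not powered to detect differences between arms. Nor do the documents give any rate at which pain fades, so the effect of a late reading cannot be put in FLACC points.

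**Conclusion.** The point holds as a defect in the schedule. The Visit 3 window as written runs from Day -2 to Day 4 and shares Day 4 with Visit 4. A child can follow the protocol fully and have no scheduled pain or inflammation reading on Days 1 to 3.

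The harm is to the early by-visit summaries of pain and inflammation and to the resolution endpoints. Cells are small: with 5 controls per procedure group, one late child is 1/5 = 20% of a control cell. The Day 45 outcome, the sample size and the comparability of the arms are not affected on anything the documents show.

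This rests on two assumptions. First, the windows mean what they say. Second, no FLACC or cell reading is taken on Day 0. The primary-endpoint text speaks of pain at every visit, which could be stretched to cover Visit 2, but neither the tables nor the Visit 2 list schedules it there.

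**What to change.** In the synopsis, Section 4.1, Tables 1 and 2 and Section 5.2.1, replace the blanket tolerance for Visit 3 with a window that is post-operative only and closes before Day 4, for example Day 1 to Day 3. Leave Visit 4 at Day 4 to Day 10 and the later visits as they are.

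Record the actual post-operative day of every FLACC and anterior chamber assessment, and add a short rule to Section 8.1:

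- A late Visit 3 stays under its visit number and is flagged as out of window.
- If two scores fall in the Visit 4 window, the one closest to Day 7 is used for the Day 7 summary. For scores on Day 4 and Day 8 the distances are 3 days and 1 day, so the Day 8 score is used.
- A tie, such as Day 4 and Day 10 (3 days each), needs a stated tie-break, for instance the score collected as Visit 4.

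Scores should not be reassigned purely by calendar day. A child seen on Day 4 as Visit 3 and on Day 8 as Visit 4 would then have two Visit 4 scores, no Visit 3 score, and no rule for choosing between them.

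The cost is wording in five places and one data field. A few Visit 3 assessments will be flagged as out of window, and some spread in timing remains within Days 1 to 3, which the recorded day makes visible.
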